2. LIST OF ABBREVIATIONS

Term	Definition / description
AE	Adverse Event
CTC	Common Terminology Criteria
CTL	Clinical Trial Leader
CTP	Clinical Trial Protocol
CTR	Clinical Trial Report
DM&SM	Boehringer Ingelheim Data Management And Statistics Manual
DRA	Drug Regulatory Affairs
DMG	Dictionary Maintenance Group
EDC	Electronic Data Capture
EMEA	European Agency For The Evaluation Of Medicinal Products
FAS	Full Analysis Set
ICH	International Conference On Harmonisation
LOCF	Last Observation Carried Forward
MedDRA	Medical Dictionary For Regulatory Activities
MQRM	Medical Quality Review Meeting
PK	Pharmacokinetics
PPS	Per Protocol Set
PSTAT	Project Statistician
PT	Preferred Term
PV	Protocol Violation
RPM	Report Planning Meeting
Q1	Lower Quartile
Q3	Upper Quartile
SA	Statistical Analysis
SD	Standard Deviation
SMQ	Standardised MedDRA Query
SOC	System Organ Class
TESS	Treatment Emergent Signs And Symptoms
ToC	Table of Contents
TMW	Trial Medical Writer
TSAP	Trial Statistical Analysis Plan

3. INTRODUCTION

As per ICH E9 ([1](#)), the purpose of this document is to provide a more technical and detailed elaboration of the principal features of the analysis described in the protocol, and to include detailed procedures for executing the statistical analysis of the primary and secondary variables and other data.

This TSAP assumes familiarity with the Clinical Trial Protocol (CTP), including Protocol Amendments. In particular, the TSAP is based on the planned analysis specification as written in CTP Section 7 “Statistical Methods and Determination of Sample Size”. Therefore, TSAP readers may consult the CTP for more background information on the study, e.g., on study objectives, study design and population, treatments, definition of measurements and variables, planning of sample size, randomization.

SAS® Version 9.4 will be used for all analyses.

4. CHANGES IN THE PLANNED ANALYSIS OF THE STUDY

There were no changes to the statistical analyses proposed in the study protocol.

5. ENDPOINTS(S)

5.1 PRIMARY ENDPOINT(S)

The primary endpoint is the occurrence of treatment emergent adverse events (TEAEs) up to Week 288.

5.2 SECONDARY ENDPOINTS

[figure not shown]
5.2.1 Key secondary endpoint(s)

[figure not shown]
This section is not applicable as no key secondary endpoint has been specified in the protocol

5.2.2 Secondary endpoint(s)

- Achievement of Psoriasis Area and Severity Index (PASI)50/PASI75/PASI90/PASI100 at Week 24
- Achievement of Static Physician's Global Assessment (sPGA) clear or almost clear at Week 24
- Achievement of sPGA clear at Week 24
- Time to loss of PASI50/PASI75/PASI90/PASI100 for patients who achieve the response up to Week 288
- Time to loss of sPGA clear or almost clear for patients who achieve the response up to Week 288
- Time to loss of sPGA clear for patients who achieve the response up to Week 288

Details for scoring Psoriasis Area and Severity Index (PASI) and static physician global assessment are described in Section 10.1 and 10.2 of the CTP. The percent reduction from baseline is calculated by % PASI reduction from baseline = ((PASI at baseline - PASI at Visit X) / PASI at baseline) * 100, at all follow up visits. Achieving an X% or larger reduction from baseline PASI score is denoted as PASIX.

6. GENERAL ANALYSIS DEFINITIONS

6.1 TREATMENT(S)

All patients need to complete the preceding Phase II psoriasis Trial 1407-0030 and meet entry criteria for this study.

Two groups of patients are to be entered into this trial, including up to (approximately) 180 patients entered in the original trial 1407-0030 protocol (now Part 1) and approximately 90 patients entered in an extended dose-ranging segment, now Part 2 of the amended trial 1407-0030 protocol. Actual numbers of subjects entering the extension trial are to be determined by response in the preceding study.

In the first group (Part 1), patients will be considered eligible to participate in this long-term extension trial upon completing the trial 1407-0030 Week 24 end-of-treatment visit with a \geq PASI50 response. BI 730357 dose levels of up to 200 mg *q.d.* are to be administered under fasting conditions to patients in this group, reflecting the dose levels evaluated during Part 1 of trial 1407-0030.

- Patients entering the extension trial will remain on their blinded BI 730357 dose treatment from the preceding trial until the open label period of 1407-0005 begins at Visit 2/Week 12.
- At Visit 2/Week 12, patients presently assigned to double blind treatment of placebo, 25 mg, 50 mg, and 100 mg will be reassigned to the 100 mg open label dose, and patients presently assigned to the double blind treatment of 200 mg will be reassigned to 200 mg open label dose.

In the second patient group (Part 2), patients will be considered eligible to participate in this trial upon completing the trial 1407-0030 Week 12 end-of-treatment visit with a \geq PASI50 response or perceived patient improvement, at the discretion of the Investigator. Patients are to be considered eligible only if also without ongoing AEs consistent with intolerance of trial medication (including gastric intolerance) that in the opinion of the investigator would compromise the safety of the patient.

.

- All patients entering the extension trial are to be assigned at Visit 1 to receive open-label treatment with 400 mg *q.d.* (fed), the anticipated therapeutic BI 730357 dose.

It is expected that Visit 1 of trial 1407-0005 will be performed on the same day of the EOT Visit of trial 1407-0030 in both patient groups. In the event that patients completing Part 2 of trial 1407-0030 are not able to be entered immediately into the extension trial due to administrative reasons (e.g., pending protocol approval, availability of trial medication), Visit 1 of the extension trial may be delayed for no more than 16 weeks.

The treatment period in this trial will be approximately 6 years.

Figure 6.1: 1

Trial 1407-0005 dose assignment/reassignment for patients entering from Part 1 of trial 1407-0030

[figure not shown]
[figure not shown]

Figure 6.1: 2

Trial 1407-0005 dose assignment for patients entering from Part 2 and continuing from Part 1 of trial 1407-0030

Dose selection at Week 12 is based on the safety and tolerability data from the SRD Trial 1407.1 and the MRD Trial 1407-0002, and will be contingent on DMC evaluation of all available data from Phase II trial 1407-0030. For patients entering from Part 1 of trial 1407-0030, if an unacceptable risk regarding the safety of the 200 mg dose level is reported by the DMC, the open label BI 730357 dose assignments beginning at Week 12, is to be altered to assign all patients to the 100 mg *q.d.* dose group.

All patients entering from Part 2 of trial 1407-0030 are to receive the 400 mg *q.d.* dose, as long as no unacceptable risks are identified during Part 2 of trial 1407-0030. Once Part 2 patients begin enrolling in this trial, existing patients receiving 100 mg *q.d.* in this trial will be given the option to titrate up to the 200 g *q.d.* dose, if the investigator determines that the Patients may benefit from the higher dose.

The first Part 2 patients enrolled in this study on December 10, 2020 and at that time all Part 1 patients had been in the study more than 12 weeks and had titrated to 100 mg *q.d.*

Subjects will be analyzed according to the treatment to which they were treated. The following study periods based on actual start and stop dates of study treatment administration are defined as follow.

Table 6.1: 1 Definition of Treatment Periods

Analysing Treatment Period	Start Date	Stop Date
Screening [#]	NA	NA
On-treatment*	Date/Time of the first administration of trial treatment	Date of the last administration of trial treatment + REP
Follow-up	Date of the last administration of trial treatment + REP+1 day	Date of the last per protocol visit

Patients in the 1407-0030 trial that fulfil the criteria for rollover will be asked to participate in this extension trial. Upon their agreement, they will immediately enter the treatment phase. Therefore, no screening period is defined in this trial.

* Within the On-treatment period, it can be divided into Period 1 (first 12 weeks) and Period 2 (after 12 weeks) for patients from part 1 of the 1407-0030 trial.

For the main safety analyses, Adverse Events (AEs) for patients who rolled over from Part 1 of trial 1407-0030 will be classified to one of the following time periods: “first 12 weeks of treatment”, “second treatment period”, or “follow up”. Section 7.3.4 of the protocol specifies that, all AEs and laboratory assessments with an onset between start of treatment and end of the residual effect period (REP), a period of 7 days after the last dose of trial medication for this trial, will be assigned to the “on-treatment” period for evaluation.

Detailed rules for assigning AEs to these time periods based on the onset dates of the AEs for patients who rolled over from Part 1 of the 1407-0030 trial are listed below (such AEs will be classified as new-onset TEAEs):

- If date of Start of Treatment visit in trial (1407-0005) \leq AE onset date $<$ date of first intake after week 12 re-assignment, then the AE is assigned to “first 12 weeks of treatment”.

If an AE occurs on the day of week 12 visit, actual time between AE onset and study medication taken will be compared to determine AE time period (first 12 weeks, second treatment period).

If the subject discontinues before the day of week 12 visit, date of first intake after week 12 re-assignment will be missing, the AE will still be assigned to “first 12 weeks of treatment”.

- If date of first intake after week 12 re-assignment \leq AE onset date \leq date of last intake + 7 days, then the AE is assigned to “second treatment period”.

Section 7.3.4 of the protocol specifies that adverse events that start before first drug intake and deteriorate under treatment will also be considered as ‘treatment emergent’. Worsening will be determined by a more severe grade according to Rheumatology Common Toxicity Criteria (RCTC) Version 2.0 Detailed rules for assigning such AEs of patients from Part 1 of the 1407-0030 trial to these time periods based on the onset dates and worsening dates of the AEs are listed below (such AEs such be classified as worsening-severity TEAEs):

- If AE onset date \leq date of End of Treatment visit in the preceding trial (1407-0030) < AE worsening date < date of first intake after week 12 re-assignment, then the AE is assigned to “first 12 weeks of treatment”.

If an AE worsening occurs on the day of week 12 visit, actual time between AE onset and study medication taken will be compared to determine AE time period (first 12 weeks, second treatment period).

If the subject discontinues before the day of week 12 visit, date of first intake after week 12 re-assignment will be missing, the AE worsening will still be assigned to “first 12 weeks of treatment”.

- If date of first intake after week 12 re-assignment \leq AE worsening date \leq date of last intake + 7 days, then the AE is assigned to “second treatment period”.

For patients who rolled over from Part 1 of the 1407-0030 trial if the onset date of an AE occurs prior to Week 12 and continues beyond Week 12 with a worsening RCTC grade after Week 12 then the AE will be captured as a TEAE both during the first 12-week period of 1407-0005 (as a new-onset TEAE) and during the second treatment period (beyond Week 12, as a worsening-TEAE).

Because there is no scheduled titration for patients who rolled over from Part 2 of trial 1407-0030 adverse events will only be summarized for the entire treatment period and will not be summarized for the first 12 weeks and after 12 weeks for these patients.

Due to differing doses, differing titration schedules and different timeframe for entering this study between patients from part 1 and part 2 of trial 1407_00030, several sets of adverse event analyses, each consisting of 11 summaries, will be presented:

- Events up to 12 weeks for patients who rolled over from Part 1 of trial 1407_00030 with treatment columns BI 25 mg, BI 50 mg, BI 100 mg and BI 200 mg
- Events after 12 weeks for patients who rolled over from Part 1 of trial 1407_00030

with treatment columns BI 25 mg/BI 100 mg, BI 50 mg/BI 100 mg, BI 100 mg/BI 100 mg and BI 200 mg/ BI 200mg.

- All events for patients who rolled over from Part 2 of trial 1407-0030 with treatment column BI 400 mg
- All events from all patients who rolled over from trial 1407-0030 (part 1 and part 2 combined) where events are classified under the treatment at onset in 1407-0005 with treatment columns BI 25 mg, BI 50 mg, BI 100 mg, BI 200 mg and BI 400 mg

Patients from part 1 of trial 1407_00030 who discontinue study treatment prior to Week 12 will be excluded from the second and fourth sets of analyses above. Due to varying length of exposure to the various doses, exposure adjusted incidence rates will be presented in addition to number and percentage of patients with events in the fifth set above (classification by dose at onset).

For the analysis of other safety data (laboratory data, vital signs ,suicidal ideation) summaries will be presented for the entire study, for the first 12 weeks of the study and after 12 weeks on study. For these outputs data from patients who rolled over from Part 1 and Part 2 of study 1407-0030 will be combined. In some of these data displays each treatment appears on a separate page. If deemed appropriate, additional displays showing descriptive statistics with figures for selected outcomes will be presented.

For efficacy summaries of response at Week 24 all patients from Part 1 of trial 1407-0030 will have data will be grouped as follows:

- 100 mg patients from part 1 of trial 1407-0030
 - 25 mg/100mg
 - 50 mg/100 mg
 - 100 mg/100mg
- 200 mg patients from part 1 of trial 1407-0030
- All patients from part 1 of trial 1407-0030
- 400 mg patients from part 2 of trial 1407-0030
- All patients from part 1 and part 2 of trial 1407-0030 combined

For efficacy summaries of time to loss of response data will be grouped as follows:

- 100 mg patients from part 1 of trial 1407-0030 (combing 25 mg/100mg, 50 mg/100 mg and 100 mg/100mg)
- 200 mg patients from part 1 of trial 1407-0030
- 400 mg patients from part 2 of trial 1407-0030

Efficacy response at Week 12 and 36 for patients from Part 2 of trial 1407-0030 will be summarized.

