5.2.6.1.2 Serious adverse event

A serious adverse event (SAE) is defined as any AE, which fulfils at least one of the following criteria:

- results in death,
- is life-threatening, which refers to an event in which the patient was at risk of death at the time of the event; it does not refer to an event that hypothetically might have caused death if more severe,
- requires inpatient hospitalisation,
- requires prolongation of existing hospitalisation,
- results in persistent or significant disability or incapacity,
- is a congenital anomaly / birth defect,
- is deemed serious for any other reason if it is an important medical event when based on appropriate medical judgement which may jeopardise the patient and may require medical or surgical intervention to prevent one of the other outcomes listed in the above definitions. Examples of such events are intensive treatment in an emergency room or at home for allergic bronchospasm, blood dyscrasias or convulsions that do not result in hospitalisation or development of dependency or abuse.

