paracoccidioides, penicillium marneffei, sporothrix schenckii, cryptosporidium species (chronic only), microsporidiosis, leishmaniasis (visceral only), trypanosoma cruzi infection (Chagas' disease) (disseminated only), campylobacteriosis (invasive only), shigellosis (invasive only), vibriosis (invasive due to vibrio vulnificus), HCV progression.

Gastric intolerance and gastritis:

Even though gastritis development is not expected in humans, AE consistent with gastric intolerance or gastritis are designated as AESI to ensure timely characterization, monitoring and reporting of any such events in this study.

Not all gastrointestinal events will be considered AESI. Only events that are consistent with the following definitions are considered AESI and will need to be reported accordingly:

- Any adverse events of "nausea or vomiting" of moderate or worse severity (according to RCTC, OR of prolonged duration (≥ 7 days), OR
- Any adverse events of "gastritis" (regardless of duration or severity)

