5.2.6.1.5 Intensity (severity) of AEs

The intensity grading of AEs will be performed according to Rheumatology Common Toxicity Criteria (RCTC) Version 2.0 developed by (R13-3515). Refer to ISF for intensity/severity classification. Intensity options are:

Grade 1 mild

Grade 2 moderate

Grade 3 severe

Grade 4 life-threatening

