7.3.4 Safety analyses

Adverse events will be coded using the Medical Dictionary for Drug Regulatory Activities (MedDRA). Standard BI summary tables and listings will be produced. All adverse events with an onset between start of treatment and end of the REP, a period of 7 days after the last dose of trial medication, will be assigned to the on-treatment period for evaluation.

All treated patients will be included in the safety analysis. In general, safety analyses will be descriptive in nature and will be based on BI standards. No hypothesis testing is planned.

Statistical analysis and reporting of adverse events will concentrate on treatment-emergent adverse events, i.e. all adverse events occurring between start of treatment and end of the REP. Adverse events that start before first drug intake and deteriorate under treatment will also be considered as 'treatment-emergent'.

Exposure-adjusted adverse event incidence rates (per the primary endpoint) will be calculated using the following approach:

• The incidence rate (per 100 subject years) of a selected adverse event (also known as the incidence density rate or person-time incidence rate) is defined as the number of subjects experiencing the adverse event per treatment group during the time at risk divided by the total time of subjects at risk in that treatment group to contribute an event to the analysis multiplied by 100 (per 100 subject years), where:

Time at risk [subject years] = (date of onset of AE – study drug start date + 1) / 365.25

If, for a subject, no treatment emergent adverse event occurred, then the time at risk will be censored at the minimum of (date of death; drug stop date + 28 days; last contact date).

For each AE, the incidence rate will therefore be calculated as:

Incidence rate [per 100 subject years (pt-yrs)] = 100 * number of subjects with TEAE / Total TEAE-specific time at risk [subject years].

Exact 95% confidence intervals (CI) around the observed AE incidence rate will also be provided.

Page 58 of 84

Frequency, severity, and causal relationship of adverse events will be tabulated by system organ class and preferred term after coding according to the current version of the Medical Dictionary for Drug Regulatory Activities (MedDRA) at database lock.

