7.8.1 Adverse Events

The analyses of adverse events will be descriptive in nature. All analyses of AEs will be based on the number of patients with AEs (not the number of AEs).

Unless otherwise specified, the analyses of AEs will be descriptive in nature. All analyses of AEs will be based on the number of subjects with AEs and NOT on the number of AEs.

The analysis of AEs will be based on the concept of treatment emergent AEs. That means that all AEs occurring between first drug intake till 7 days after last drug intake will be assigned to the received treatment. All AEs occurring before first drug intake will be assigned to 'screening' and all AEs occurring after last drug intake + 7 days will be assigned to 'follow-up' (for listings only). For details on the treatment definition, see [Section 6.1](#).

According to ICH E3 [\(5\)](#), in addition to Deaths and serious adverse events, 'other significant' AEs need to be listed in the clinical trial report. These will be any non-serious adverse event that led to an action taken with study drug (e.g. discontinuation or dose reduced or interrupted). An overall summary of adverse events will be presented.

The frequency of subjects with AEs will be summarised by treatment, primary system organ class and PT using the version of MedDRA at the database lock. Separate tables will be provided for subjects with SAEs, AEs leading to treatment discontinuation and related AEs.

The system organ classes will be sorted by default by decreasing frequency and PTs will be sorted by decreasing frequency within SOC.

For further details on summarization of AE data, please refer to the guideline 'Handling and summarization of adverse event data for clinical trial reports and integrated summaries' [\(4\)](#).

The severity of AEs will be summarised by the maximum intensity of the events each patient had (as indicated by the recorded RCTC version 2 grade). This will show the number and percent of patients who had at most mild, moderate, severe, and life threatening events. Severe adverse event is defined as an AE with RCTC grade equals to 3 (severe) or 4 (life threatening).

Groupings of adverse events and adverse events of special interest (AESI)

The AESI have been defined in the protocol.

Other user-defined special adverse event grouped term for BI 730357 specified in the following [Table 7.8.1:1](#).

Table 7.8.1: 1 User Defined Adverse Event Group Terms

N	Term	Definition #

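### SAP 6.1 recognises worsening only as a higher RCTC grade, so an AE ongoing at first intake that becomes serious or fatal at an unchanged grade can be missing from the TEAE and SAE tables

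*SAP*

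**What the plan says.** Protocol 7.3.4 extends the TEAE definition beyond new events. It adds "Adverse events that start before first drug intake and deteriorate under treatment", and it does not say how deterioration is to be measured.

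SAP 6.1 supplies the measure: "Worsening will be determined by a more severe grade according to Rheumatology Common Toxicity Criteria (RCTC) Version 2.0". No other criterion is given. The detailed date rules that follow are written for Part 1. They place a carried-over event in the first 12 weeks or in the second period by its worsening date. Part 2 has a single treatment period and no rules of its own, but the sentence on grade is not limited to Part 1.

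For Part 1 events that start before Week 12, SAP 6.1 uses the same test: an event that "continues beyond Week 12 with a worsening RCTC grade after Week 12 then the AE will be captured as a TEAE both" in the first period, as new-onset, and in the second, as worsening.

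SAP 7.8.1 states: "The analysis of AEs will be based on the concept of treatment emergent AEs". It sends events occurring before first intake to a screening category, apparently for listings only. The SAE tables belong to this TEAE-based analysis. SAP 4 declares no change from the protocol's analyses.

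**The concern.** The protocol keeps grade and seriousness apart. Seriousness (Protocol 5.2.6.1.2) turns on outcomes such as an event that "requires inpatient hospitalisation", not on a grade. The intensity scale (Protocol 5.2.6.1.5) ends at "Grade 4 life-threatening", so an event already at the top cannot rise when it becomes fatal. A grade-only test therefore cannot register two plain forms of deterioration.

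Patients can enter with ongoing events. Exclusion criterion 14 bars only ongoing intolerance of trial medication that the investigator judges would compromise safety. The synopsis is stricter, but it covers only AEs related to trial medication. On either wording, a patient with an unrelated ongoing event may enter. In Part 2, patients who were on placebo may start 400 mg at Visit 1, so an event carried over from placebo may deteriorate on active drug.

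The primary endpoint is the occurrence of TEAEs, and the trial is meant to support registration. A serious or fatal deterioration on treatment should not drop out of the by-dose tables because its grade stayed the same.

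**Working it through.** The plan states no figure on this point and tests no hypothesis, so the check applies the written rules to example events.

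**Rules used**

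- New-onset TEAE (SAP 6.1): onset from the start of treatment in 1407-0005 to last intake + 7 days. In Part 1, the first intake after Week 12 re-assignment divides the two periods.
- Worsening TEAE (SAP 6.1): earlier onset, with a higher RCTC grade dated within the period.
- An event that meets neither rule in a period is not placed in that period's tables.

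**Hypothetical events**, with first open-label intake assumed on Day 85 and no new AE record opened:

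1. Onset in 1407-0030 at Grade 2; hospitalised on Day 30, still Grade 2. Not new-onset and no grade rise. It is in no TEAE or SAE table. The same result follows for a Part 2 patient.
2. Onset Day 40 at Grade 3; hospitalised on Day 100, still Grade 3. New-onset in the first 12 weeks, so it is counted there under the first-period dose, and in the combined set by dose at onset. It is absent from the after-Week-12 set.
3. Onset Day 70 at Grade 4; fatal on Day 95. No higher grade exists. Same result as event 2.
4. Control: onset before Week 12 at Grade 2; Grade 3 after Week 12. Counted in both periods, as SAP 6.1 intends.

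**Comparison with the protocol.** Protocol 7.3.4 speaks only of events that start before first intake. Event 1 falls under that sentence, and the SAP's test is narrower than the protocol's wording. Events 2 and 3 start after first intake and are already treatment-emergent under the protocol, which has no rule for counting them again after Week 12. The SAP's second count goes beyond the protocol there.

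**Effect on the exposure-adjusted rate (SAP 7.4.1).** In event 1 the patient is not in the numerator for that preferred term, and contributes time at risk up to the censoring date. Events 2 and 3 are already counted at first onset, so a later change at the same grade does not alter a rate calculated over the whole treatment period.

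**Scale.** The number of such events cannot be computed from the documents. The protocol synopsis gives 0 to 90 patients on 400 mg. At the upper end, one affected patient changes a percentage in that column by 1/90 = 1.1 percentage points. This is the weight of one patient, not an estimate of frequency.

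**The case against.** The strongest reply has four parts.

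- **A SAP is meant to make the protocol operational.** Grade is a reproducible way to define deterioration. This stands as a defence of keeping the grade rule. It does not make that rule able to register a fatal outcome at Grade 4 or a same-grade change to serious.
- **Sites may open a new record.** Protocol 5.2.6.1.1 asks for worsening of pre-existing conditions to be recorded as an AE, and Protocol 8.3.1 requires an onset date for SAEs. With a new record and a new onset date, event 1 would be a new-onset TEAE. The documents do not settle this. SAP 6.1 works with a worsening date on an event that has an earlier onset, and the AE-handling guideline cited in SAP 7.8.1 is not available here. The detailed RCTC criteria are not available either, so how often a hospitalisation leaves the grade unchanged cannot be checked.
- **Other safeguards exist.** Deaths and SAEs are listed, suicidal behaviour and type 4 or 5 ideation are reported as separate SAEs, and adjudicated MACE is summarised separately. These limit the harm, but listings do not enter the by-dose tables or rates.
- **The case is rare.** Exclusion criteria 10 and 11 make entry with an ongoing life-threatening event unlikely. The same-grade change to serious is the more realistic route.

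Stronger readings are tempting, and the documents do not support them:

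- A reader might infer that the SAP departs from Protocol 7.3.4 at Week 12, or that events crossing Week 12 vanish. Neither follows, as events 2 and 3 show.
- A reader might infer that mild nausea which becomes an AESI through the "OR of prolonged duration" route (Protocol 5.2.6.1.4) is another lost deterioration. Persistence at the same mild grade is not clearly deterioration.
- A reader might infer a systematic undercount at higher doses. The 100/100 mg and 200/200 mg groups have no scheduled dose increase at Week 12, and Part 2 has one period. Attribution to a lower dose at the Week 12 change concerns the 25/100 mg and 50/100 mg groups.

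**Conclusion.** The point holds in a narrow form. As written, SAP 6.1 can leave an AE that was ongoing at first intake in 1407-0005, and that becomes serious or fatal on treatment at an unchanged grade, outside the TEAE and SAE tables. This applies to both Parts. It assumes that the site does not open a new AE record and that the RCTC grade can stay the same when the event becomes serious; neither can be confirmed from the documents.

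For Part 1 events that start in the first 12 weeks, the effect is attribution to the earlier period and, in some groups, the lower dose. Nothing is lost from the report.

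The number of affected patients is unknown and probably small. The change is still worth making, because the omission concerns serious and fatal events in a trial whose primary endpoint is TEAEs.

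**What to change.** In SAP 6.1, define worsening as any of: a higher RCTC grade; a change from non-serious to serious; or a fatal outcome. Use the date of that change as the worsening date (for the last two, the SAE onset date or the date of death), and let it assign the period. State that this applies to events ongoing at first intake in both Part 1 and Part 2, and use the same definition in the sentence on events that continue beyond Week 12. It would also help to state whether a site opens a new AE record when an ongoing event becomes serious.

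The grade rule stays, and the added criteria need a short text change and some programming. A few more TEAEs will be counted. The main practical cost is the date: Protocol 8.3.1 names onset and end dates for AEs and SAEs, but no date on which an existing event became serious. That date must be available in the database or taken from the SAE record.
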